8. RESEARCH QUESTION AND OBJECTIVES

8.1. Research Question

The research question of this study is to characterize how nusinersen may affect pregnancy outcomes and infants born to individuals with SMA who were exposed to nusinersen during a relevant window. For the purposes of this study, "relevant window" and "relevant exposure window" are defined as 14 months prior to the first day of the participant's LMP before conception, 14.5 months before the date of conception, and/or at any time during their pregnancy.

8.2. Primary Objectives

The primary objectives of the study are:

- To prospectively evaluate pregnancy complications and outcomes in individuals with SMA who were exposed to nusinersen up to 14 months prior to the first day of their last menstrual period before conception, 14.5 months before the date of conception, and/or at any time during their pregnancy.
- To prospectively evaluate birth outcomes and adverse effects in infants born to individuals with SMA who were exposed to nusinersen up to 14 months prior to the first day of their LMP before conception, 14.5 months before the date of conception, and/or at any time during their pregnancy.

The pregnancy and infant outcomes are described in Section 8.2.1 and further defined in Section 9.3.

8.2.1. Pregnancy and Infant Outcomes

Pregnancy outcomes include pregnancy loss (pregnancy termination, spontaneous abortion, and fetal death [stillbirth]) and live birth (premature birth and full-term birth). Within each of these categories, the fetus or infant will be evaluated as to the presence or absence of anomalies or other fetal effects.

Pregnancy Loss

- Pregnancy termination (any induced or voluntary fetal loss during pregnancy)
- Spontaneous abortion (< 20 weeks of gestation)
- Fetal death, including stillbirth (fetuses born dead at ≥ 20 weeks of gestation or fetuses born dead at ≥ 350 g if gestational age is unknown), which is further classified as follows:
 - Early fetal loss (fetal death occurring at ≥ 20 weeks but ≤ 28 weeks of gestation)
 - Late fetal loss (occurring at \geq 28 weeks of gestation)

Live Birth

• Premature birth (delivered < 37 weeks)

CONFIDENTIAL

• Full term birth (delivered \geq 37 weeks)

Infant deaths up to 52 weeks of age, as defined in Section 9.3, will be reported among live births.

Major Congenital Malformations

- Interchangeably referred to as congenital malformations, congenital anomalies, and birth defects.
- Abnormalities in structural development that are medically or cosmetically significant, are present at birth, and persist in postnatal life unless or until repaired, as evaluated by independent advisors.

In addition, SGA births, abnormal postnatal growth and development (i.e., social/emotional, language/communication, neurocognitive, movement/physical development milestones) up to 2 years of age, ectopic pregnancies, and molar pregnancies will be reported for each pregnancy outcome (see Section 9.3). Given that SMA is a genetic condition, it is possible that babies born to an individual with SMA will also have SMA. Therefore, the diagnosis of SMA in infants will also be collected.

Maternal death during pregnancy, labor, delivery, or up to 12 weeks after delivery will be reported. Infant deaths occurring up to 52 weeks of age will also be reported.

8.3. Secondary Objectives

The secondary objective of the study is to evaluate pregnancy outcomes in individuals with SMA exposed to nusinersen as compared with individuals without SMA who were not exposed to nusinersen (e.g., individuals from external, general population comparators).

9. RESEARCH METHODS

9.1. Study Design

This is an observational cohort study utilizing data within existing SMA registries designed to evaluate pregnancy and birth outcomes in women with SMA who were exposed to nusinersen (see Section 9.3 for variables collected and reported during the study).

In an effort to ensure that this study collects, analyzes, and presents information that is accurate and useful to HCPs and others, the study will conform to the US FDA Guidance for Industry on Postapproval Pregnancy Safety Studies [FDA 2019].

9.2. Setting

Patients with SMA who are enrolled in the ISMAR-US, UK Adult SMA-REACH, and SMArtCARE SMA registries will be informed of the pregnancy study and encouraged to participate if they become pregnant within the relevant exposure window for nusinersen. The registries will collect information on the pregnancy and birth outcomes.

Reporting of pregnancy exposures to nusinersen is voluntary. Pregnancies should be reported as early as possible, ideally before prenatal testing beyond confirmatory pregnancy tests (e.g., alpha fetoprotein, sonography, amniocentesis) has been performed, but pregnancies that are reported after informative prenatal testing has been conducted will also be included in the study. Patients who test positive for a medical condition associated with negative pregnancy outcomes (e.g., syphilis) may also enroll in the study. Pregnancies with known outcomes at the time of the initial report (i.e., retrospective cases) will be included in this study but will be analyzed separately from cases in which the pregnancy outcome is unknown at the time of enrollment (i.e., prospective cases).

Pregnancies in partners of male patients who were exposed to nusinersen will not be included in the study but will be collected according to standard postmarketing pharmacovigilance practice.

The eligibility criteria and data captured in the study are intended to be uniform across all countries in which the study will be conducted. Any changes to eligibility criteria or data collection imposed by a local IRB or ethics committee will be noted in interim and final study reports.

Scientific oversight of the pregnancy study will be the responsibility of Biogen Epidemiology, while data collection and conduct of the ongoing registries will be managed by the registries.

9.2.1. Study Contact Schedule

There are no mandated physician visits for this study. Instead, it is expected that participants and HCPs will be contacted according to the recommended study contact schedule (Section 16). While contacts for this study are not mandated, registries will inform participants and HCPs of the expected contact schedule and make every effort to ensure data are entered for each expected contact. The registries will also utilize

CONFIDENTIAL

electronic medical record review to collect data when contacting participants/HCPs is not feasible.

Pregnancy information will be collected by the registries from HCPs to determine eligibility. The registries will obtain informed consent for the pregnancy study (if not already adequately covered by the existing registry consent) prior to collecting data from the participant for the study.

After the participant enrolled in the registry provides consent for the pregnancy study, current demographic data, contact information, and pregnancy information, in addition to relevant medical history at the time the pregnancy is reported, will be collected. The contact information will be confidential and remain on site. Thereafter, it is expected that the participant will be contacted once per trimester to update contact information and ascertain the occurrence of a pregnancy outcome. It is expected that the participant's obstetric HCP will be contacted at 6 to 7 months of gestation for the Prenatal Follow-Up and at approximately 4 weeks after the EDD for the Pregnancy Outcome Follow-Up. At approximately 1, 2, 6, 12, 18, and 24 months after birth, it is expected that the pediatric HCP (or the participant) will be contacted for a Pediatric Follow-Up. All data collected will be entered into the registry. See Table 4 for a description of the expected contacts with participants and HCPs.

If the participant experiences an adverse pregnancy outcome or has a pregnancy termination or an abortion of unknown cause, the HCP is encouraged to report this outcome as soon as possible rather than to wait until the scheduled follow-up contact.

See Section 9.3.2 and Table 5 for the recommended information to be collected at different periods.

9.2.2. Study Population

To be eligible to participate in this study, candidates must meet the following eligibility criteria at the time the pregnancy is reported.

9.2.2.1. Inclusion Criteria

- 1. Individual who is currently pregnant (or was pregnant during the relevant exposure window; see inclusion criterion 4) and enrolled in the ISMAR-US, UK Adult SMA-REACH, or the Germany, Austria, or Switzerland network of the SMArtCARE registry.
- 2. Ability of the participant and/or their legally authorized representative (e.g., parent, spouse, or legal guardian), as appropriate and where allowed by local regulations, to understand the purpose and risks of the study, to provide informed consent, and to authorize the use of confidential health information in accordance with national and local privacy regulations.
- 3. Genetic documentation of 5q SMA.
- 4. Documentation that the participant was exposed to nusinersen up to 14 months prior to the first day of their LMP before conception, 14.5 months before conception, and/or at any time during their pregnancy. If exact exposure dates are CONFIDENTIAL

unknown, the reporter must be able to estimate either the months of exposure during pregnancy or the trimester of exposure.

5. Agreement to release medical information, thereby permitting the registry to contact the participant's HCPs and the pediatric HCP for medical information.

9.2.2.2. Exclusion Criteria

- 1. Inability to comply with study requirements.
- 2. Other unspecified reasons that, in the opinion of the HCP, registry, or Biogen, make the patient unsuitable for enrollment.
- 3. Treatment with risdiplam at any time from the first day of their LMP, 2 weeks prior to the date of conception (approximately 5 half-lives), and/or plans to receive treatment with risdiplam during pregnancy.

9.2.3. Study Location

The study will be conducted in the US, UK, Germany, Austria, and Switzerland.

9.2.4. Study Duration

This study will be conducted for a minimum of 10 years from initiation of the first registry partnership for this study.

Each participant enrolled will be followed until the end of their pregnancy and for up to 12 weeks after delivery. Each infant will be followed for approximately 2 years after birth.

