9.3.1.8. Maternal Death

The study defines maternal death as death of a pregnant individual during pregnancy, labor, or delivery. The study will also report maternal deaths that occur up to 12 weeks after delivery. In the event of maternal death, full pathology details will be requested.

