9.3.2.5. Pediatric Follow-up

It is expected that the following information will be collected from the pediatric HCP (or the participant, as necessary) when the infant is approximately 1, 2, 6, 12, 18, and 24 months of age:

- Pediatric illnesses (e.g., prematurity, respiratory dysfunction, birth trauma) that resulted in hospitalization, including any treatments (e.g., drug therapies)
- Infant characteristics
 - Head circumference
 - Feeding behavior
 - Weight and length
 - Developmental milestones (including postnatal growth deficiency or failure to thrive [FTT], infant development deficiency, and neurobehavioral impairment). Note: neurobehavioral impairment will be measured starting at 2 months of age.
 - Breastfeeding status (whether the infant is breastfeeding, bottle-fed, or both, as well as duration of breastfeeding, if applicable)
 - Genetic diagnoses, including SMA
 - Medications
- Evidence of any abnormality since last follow-up

Additional information and reports will be requested and collected for adverse pregnancy outcomes in the mother (i.e., death up to 12 weeks after delivery) and infant as necessary, including autopsy and other pathology reports.

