9.7. Data Analysis

9.7.1. General Discussion of the Analysis

All participants will be reviewed based on earliest exposure within the relevant nusinersen exposure window.

The registries and Biogen Epidemiology and Global Safety will carefully review each pregnancy outcome and the frequency of adverse pregnancy outcomes. For this study, gestational weeks are calculated beginning from the first day of the participant's LMP. If the date of LMP is not available, the EDD may be used. If the gestational week is

inconsistent with the exposure dates and/or the dates of outcomes (outside of 1 week for the first trimester, outside of 2 weeks for the second and third trimesters) and a corrected EDD (i.e., generally by ultrasound) is available, the corrected EDD is used for gestational week calculations.

Descriptive analyses will be performed to analyze the risks of MCMs, spontaneous abortions, SGA births, and abnormal postnatal growth and development.

Statistical analyses may be performed to examine potential increases in risks of MCMs, spontaneous abortions, SGA births, and abnormal postnatal growth and development as compared with the expected background prevalence. The prevalence and 95% CIs for study participants may be calculated to assess the presence of any excessive risk associated with nusinersen exposure.

All analyses will be conducted on an overall basis as well as grouped by the earliest trimester of exposure. For MCMs, analyses will be conducted only for participants who have exposure in the first trimester. In the absence of treatment initiation during the second and third trimester of pregnancy, the subgroups with small sample sizes may be collapsed as needed. Other adverse pregnancy outcomes will be examined similarly as the sample size permits.

A periodic review of the study will be performed by monitoring reports of adverse pregnancy outcomes for nusinersen (see Section 9.7.4).

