16. ANNEX 3: RECOMMENDED STUDY CONTACT SCHEDULE

Table 4: Expected Contacts With Participants and HCPs

Expected Contacts ¹ with Participant	Expected Contacts ¹ with Participant's HCP (e.g., Obstetrician)	Expected Contacts ¹ With Pediatric HCP (e.g., Pediatrician) ²
Enrollment	Enrollment	1, 2, 6, 12, 18, and 24 months of age ⁵ : for
First trimester ³ : for pregnancy status follow-up Second trimester ³ : for pregnancy status follow-up	6 to 7 months of gestation: for Prenatal Follow-Up 4 weeks after EDD ⁴ : for Pregnancy Outcome Follow-Up	Pediatric Follow-Up
Third trimester ³ : for pregnancy status follow-up		

Contacts for this study are not mandated, but registries will inform participants and HCPs of the expected contact schedule and make every effort to ensure data are entered for each expected contact.

² Live births only.

³ Follow up with the HCP, if needed.

⁴ Follow up with other practitioners or the participant, if needed.

⁵ Follow up with the participant, if needed.

Table 5: Recommended Study Contact Schedule

	Enrollment	Prenatal	Prenatal Follow-Up		Pediatric Follow-Up
Data Collection	Initial Report/Registration by Participant and/or HCP ¹	Contact Participant or HCP at Each Trimester	Contact HCP at Approximately 6 to 7 Months of Gestation	Contact HCP(s) at Approximately 4 Weeks After EDD ²	Contact Pediatric HCP at Approximately 1, 2, 6, 12, 18, and 24 Months of Age ³
Informed Consent ⁴	X				
Participant Demographics	X				
Participant Contact Information and Secondary Contact Information	Х	X	Х		
Medical History	X		X		
Pregnancy History and Current Pregnancy Information ⁵	X				
Pregnancy Outcome Risk Factors ⁶	X	X	X	X	
Prenatal Testing	X		X		
Current Pregnancy Status	X	X	X		
Gestational Age (in Weeks)		X	X	X	
Weight Gain During Pregnancy		X	X	X	
Nusinersen Exposure History and Adherence	X	X	X	X	

Data Collection	Enrollment Initial Report/Registration by Participant and/or HCP ¹	Prenatal Follow-Up		Pregnancy Outcome Follow-Up	Pediatric Follow-Up
		Contact Participant or HCP at Each Trimester	Contact HCP at Approximately 6 to 7 Months of Gestation	Contact HCP(s) at Approximately 4 Weeks After EDD ²	Contact Pediatric HCP at Approximately 1, 2, 6, 12, 18, and 24 Months of Age ³
Prior and Current Medications Other Than Nusinersen	X ⁷	X	X	X	
Possible SMA Symptoms ⁸			X	X	
Pregnancy Outcome				X	
Type of Delivery				X ⁹	
Complications During Pregnancy and/or Birth with Associated Notable Dates		X	X	X	
Neonatal or Pediatric Illness ¹⁰				X	X

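### Maternal death is to be reported to 12 weeks after delivery, but no scheduled contact records the mother's vital status at or after week 12

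*Protocol*

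**What the plan says.** The commitment appears in several places. Section 9.2.4: "Each participant enrolled will be followed until the end of their pregnancy and for up to 12 weeks after delivery". Section 9.3.1.8, after defining maternal death in pregnancy, labor and delivery: "The study will also report maternal deaths that occur up to 12 weeks after delivery". The abstract and section 8.2.1 list the same 12-week outcome. Section 7.2.3 gives the same follow-up period and applies it to complications as well as outcomes.

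The contacts are set in section 9.2.1, section 9.3.2 and Annex 3:

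- **Participant.** Table 4 lists enrollment and one contact per trimester, "for pregnancy status follow-up". The third-trimester contact is the last one addressed to her.
- **Her own clinician.** The last contact is "at approximately 4 weeks after the EDD for the Pregnancy Outcome Follow-Up" (section 9.2.1), with other practitioners or the participant as back-up.
- **Pediatric contacts.** Section 9.3.2.5 names the "pediatric HCP (or the participant, as necessary) when the infant is approximately 1, 2, 6, 12, 18, and 24" months of age. Table 4 restricts these to "Live births only".
- **Maternal death within pediatric follow-up.** Section 9.3.2.5 closes by providing for further information and reports, where necessary, on "adverse pregnancy outcomes in the mother (i.e., death up to 12 weeks after delivery"). Its item list, and the legible pediatric column of Table 5, contain infant items only.

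**The concern.** Maternal death over a stated window is a listed outcome. To count it, the study must know for each woman whether she was alive when the window closed. The contacts that concern the mother end at a date tied to the EDD, and for a term delivery that date falls well inside the 12 weeks. The later contacts concern the infant, and no listed item asks about the mother.

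At stake is the meaning of the reported count. The sponsor receives aggregate tables only (section 9.4), and section 11 requires no expedited reporting of adverse events, so neither route makes up for a missing item. With about 20 pregnancies expected (section 9.5), one missed death is the difference between 0/20 and 1/20 = 5%.

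**Working it through.** The protocol gives no coverage figure to reproduce. The check is calendar arithmetic.

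**Inputs**
- Window: 12 weeks after delivery (sections 9.2.4, 9.3.1.8).
- Last scheduled contact with the woman's own clinician: about EDD + 4 weeks (section 9.2.1, Tables 4 and 5).
- Clock: "gestational weeks are calculated beginning from the first day of the participant's LMP" (section 9.7.1).
- Assumption: EDD = 40 weeks. This is the usual convention; the protocol does not state it.
- Pediatric contacts: 1, 2 and 6 months after birth, then later (section 9.3.2.5).

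**Step 1: coverage by the outcome follow-up.** The contact falls at gestational week 40 + 4 = 44. For delivery at week G, weeks covered = 44 − G (at most 12), and the remaining tail = 12 − (44 − G) = G − 32 when G > 32.

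| Delivery at week | Weeks covered | Tail (weeks) | Tail as share of 12 weeks |
|---|---|---|---|
| 32 | 12 | 0 | 0% |
| 34 | 10 | 2 | 17% |
| 37 | 7 | 5 | 42% |
| 39 | 5 | 7 | 58% |
| 40 | 4 | 8 | 67% |
| 41 | 3 | 9 | 75% |

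Full coverage needs 44 − G ≥ 12, so G ≤ 32. Each week by which the EDD convention or the actual contact date differs moves these figures by one week: a contact at week 43 gives a limit of 31, and at week 45 a limit of 33.

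**Step 2: later contacts after a live birth.** Months convert to weeks as months × 365.25 / 12 / 7.
- 1 month = 4.3 weeks: inside the window.
- 2 months = 8.7 weeks: inside the window.
- 6 months = 26.1 weeks: after the window has closed.

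The 6-month contact is thus the first scheduled one that could settle 12-week status. No listed item asks it to.

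**Step 3: pregnancies without a live birth.** The pediatric contacts do not apply, so the outcome follow-up is the last scheduled contact. After a stillbirth at 38 weeks it would come 44 − 38 = 6 weeks later if held on schedule. It may come sooner: section 9.2.1 encourages prompt reporting of adverse outcomes, and section 9.3.2.4 has the registry approach the clinician early. A loss at 30 weeks would be covered for 44 − 30 = 14 weeks on the nominal schedule, but for only days if the outcome contact is made at once. The 32-week limit therefore does not hold reliably for losses.

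**Step 4: other routes.** Section 9.2.5 requires monthly attempts for 6 months after the EDD, but only while the pregnancy outcome is missing. Section 9.2.1 allows record review where contact is not feasible. Neither is tied to maternal status at 12 weeks.

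**The case against.** A reader might infer that the end of the window is simply unobserved, or that a late stillbirth is followed by no contact of any kind. The protocol does not support either reading. After a live birth, the pediatric clinician or the participant is approached at 1, 2 and 6 months, and the last of these comes after the window. Section 9.3.2.5 names maternal death to 12 weeks explicitly. Record review is permitted, and the women belong to continuing SMA registries. After a loss, sections 9.3.1.1.3 and 9.3.2.4 provide for pathology details and additional reports. These routes are real. What they lack is a routine question: requesting further reports as needed does not require anyone to establish each woman's status.

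A reader might also take the 42% to 75% tail as the share of deaths that would be missed. It is only the share of the window that falls after the last scheduled contact with her own clinician.

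Nor does the gap extend to pregnancy complications generally. Section 9.3.1.14 lists pre-eclampsia, pregnancy-induced hypertension, preterm labor, gestational diabetes and placenta previa. The last three belong to pregnancy itself and are within reach of the outcome follow-up. The shortfall is mainly hypertensive disease appearing late after delivery.

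Table 5 also has a row for pregnancy-related serious adverse events in which no marks are legible. If its marks cover the pediatric column, that row could provide part of what is missing, so it should be checked. Nothing here relies on that row being empty.

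Materiality is limited, and this stands. Maternal death is not among the outcomes assigned a prevalence and confidence interval in section 9.7.3. Even with complete ascertainment, 0/20 has an exact two-sided 95% upper limit of 1 − 0.025^(1/20) = 16.8%. The contact schedule is recommended, not mandated. However, the items to be collected are set in this protocol, and an analysis plan cannot recover a status that was never recorded.

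**Conclusion.** The point holds in a limited form. The protocol commits to maternal-death reporting through 12 weeks after delivery, and its legible schedule contains no maternal vital-status item at or after that time. With EDD = 40 weeks and the outcome follow-up held on time, the last scheduled contact with the woman's own clinician covers 3 to 7 of the 12 weeks for deliveries at 41 to 37 weeks, and all 12 only at 32 weeks or earlier. Losses reported early may be covered for less.

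After a live birth the remaining weeks can be observed, but not systematically. After any other outcome, no scheduled contact follows the outcome follow-up. A zero count would then be ambiguous. No formal inference depends on it, so this is a cheap improvement that makes a listed outcome ascertainable over its own window.

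**What to change.** 1. In section 9.3.2.5 and the pediatric column of Table 5, add maternal vital status through 12 weeks after delivery, with the date of any death and any late postpartum hypertensive complication, to the existing 6-month contact.
2. For pregnancies that end without a live birth, add one registry check (participant, clinician or medical record) at about 12 weeks after the actual end of pregnancy, not after the EDD. The same check would serve where an infant dies before the 6-month contact.
3. Report maternal deaths beside the number of women whose 12-week status is known.

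The cost is one data item at a contact already planned, a few record checks among about 20 expected pregnancies, and a short amendment. No mandated visit is added.
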